## **12.9 Safety Analysis**

## 12.9.1 Adverse Events

AE terms will be coded using MedDRA dictionary. A treatment-emergent AE (TEAE) is defined as an AE that starts after the first dose of study medication through 5 days after the last dose. If relationship to treatment is missing, the event will be conservatively considered as being related to study drug. If severity is missing, a separate category of missing severity will be included in the summary table, and no imputation of severity will be performed. Through the data cleaning process, all attempts will be made to avoid missing values for relationship and severity.

All AEs will be presented in a by-treatment and by-subject listing, detailing the verbatim term given by the investigator, the preferred term (PT), system organ class (SOC), onset date and time, end date and time, intensity, outcome, relationship to study drug/treatment, action taken with study drug/treatment, other action taken to treat the event, seriousness and criteria for seriousness. Serious AEs (SAEs) and TEAEs leading to study discontinuation will also be presented in a separate listing. Deaths and non-fatal SAEs will be listed by subject and tabulated by PT.

Each TEAE will be identified as titration period AE or treatment period AE according to the following rules:

- PPC-06 400 mg QD:
  - Any TEAE starting before Day 15 is considered as a titration period AE
  - Any TEAE starting on or after Day 15 is considered as a treatment period AE
- PPC-06 400 mg BID, PPC-06 600 mg BID:
  - Any TEAE starting before Day 36 is considered as a titration period AE
  - Any TEAE starting on or after Day 36 is consider as a treatment period AE
- Placebo BID:
  - No study period will be further designated for this group. They should match equivalent phases to calculate therapeutic effect for eg: for 400 mg it should be Day 15 and >15 days, for other doses it should be Day 36 and >36 days.

An overall summary of AEs will be presented by treatment and overall, for the titration period, treatment period, and overall. The summary will include the total number of events, frequency counts and percentages, and exposure-adjusted incidence rate for:

- Any AE
- Any TEAE
- Any serious TEAE
- Any treatment-related TEAE, including definitely, probably, and possibly related
- Any TEAE leading to study drug discontinuation
- Any SAEs (non-Fatal)
- Any Deaths

For the 3 arms receiving active treatment, exposure-adjusted incidence rate will be defined for both titration and treatment periods as number of subjects with AEs divided by total number of subject-days with exposure to study medication. Total number of subject-days with exposure in each period = sum of durations in days across all subjects in each period. Duration in each period is defined as following:

- PPC-06 400 mg QD:
  - Titration period = Number of days between date of first study application and the earlier of date of last study medication and Day 14 inclusive
  - Treatment period = Number of days between Day 15 and date of last study application inclusive
- PPC-06 400 mg BID, PPC-06 600 mg BID:
  - Titration period = Number of days between date of first study application and the earlier of date of last study medication and Day 35 inclusive
  - Treatment period = Number of days between Day 36 and date of last study application inclusive

Summaries of the incidence of TEAEs will be displayed by treatment according to the following:

- All TEAEs by SOC in alphabetical order and PT in descending order of frequency (the combined frequency in the three active treatments)
- All TEAEs by SOC, PT, and maximum severity (mild, moderate, or severe)
- All TEAEs by SOC, PT, and maximum causality (not related, related) to the study drug

At each level of summarization, a subject will be counted once if he/she reported one or more events. In the counts of subjects with TEAEs, each subject will contribute only once (maximum severity) regardless of the number of occurrences (events).

The severity of TEAEs and relationship to study drug will be summarized in a similar manner. For summaries of relationship to study drug, a subject will be classified according to the closest relationship. For summaries of TEAE severity, a subject will be classified according to the highest severity.

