4. STUDY DESIGN

4.1 Overall Study Design

This is a Phase 2, randomized, double-blind, placebo-controlled, multicenter study designed to assess the safety and efficacy of PPC-06 in subjects with moderate-to-severe plaque psoriasis. Study subjects will be enrolled at approximately 75 sites in the United States (US).

Approximately 400 subjects who meet the study entry criteria will be randomly assigned in a 1:1:1:1 ratio to 1 of the 4 treatment arms:

1. PPC-06 400 mg once daily (QD)
2. PPC-06 400 mg BID
3. PPC-06 600 mg BID
4. Placebo BID

The maximum study duration for each subject will be approximately 29 weeks. The study will include an up-to-4-week screening phase (which can be extended if necessary on a case-by-case

[figure not shown]
basis for washout of prohibited prior medication), a 24-week treatment phase (that includes a 5-week titration phase and a 19-week treatment period at the maintenance dose), and a 1-visit, 1-week End-of-Study (EOS) Safety Follow-up Period. If necessary, the Investigator may decide to extend the EOS beyond 1 week to monitor recovery of safety parameters (eg, lymphopenia).

Blood samples for PD assessments will be collected at baseline and at Weeks 4, 8, 12, 16, 20, and 24. PD assessments will be conducted in all subjects, with the intent of evaluating psoriasis-associated inflammatory markers. Details of PD assessment will be provided in a separate protocol.

Subjects who discontinue study drug for more than 2 consecutive weeks due to tolerability issues or for any other reason at any point during the study will not be allowed to resume treatment with study drug and will be scheduled for the early termination visit (ETV). For those subjects where the ETV occurs 1 week or more post the last study drug dose, the safety follow up visit is not required. Subjects who discontinue from the study for any other reason at any time point will directly continue to the ETV and then enter the EOS Safety Follow-up period (if required).

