6.2 Dosing Regimen

Dosages and pill allocations for the Titration Period (Weeks 1-5) and for the Treatment Period (Weeks 6-24) are shown in [Table 6-1](#) and [Table 6-3](#), respectively. The dosing regimen for the Titration Period is presented in [Table 6-2](#). Note: Doses specified in red followed by a 'P' indicate Placebo.

Double-Blind Titration Period (Baseline through Week 5)

Following completion of the pre-randomization Screening Period, eligible subjects will be randomized in a 1:1:1:1 ratio to 1 of the 4 treatment arms and will enter the 5-week Double-Blind Titration Period. The first dose of study drug will be taken the day after the Baseline Visit (on Day 1). If a subject misses a dose (or several doses) during the Titration Period, they should skip that dose and continue with the next scheduled dose. At least 4 hours should elapse between doses, but ideally 8-12 hour intervals should be maintained. If a subject misses 7 or more consecutive days of dosing during the Titration Period, the site should contact the Sponsor or designee for guidance on how to proceed. At Visit 3 (Week 4), the subjects will

be instructed to continue 1 more week of Titration dose (Week 5 of blister wallets) and will also be given a kit of bottles which will allow dosing until Visit 4. Please refer to [Table 6-1](#) for titration schedule.

Double-Blind Treatment Period (Week 6 through Week 24)

Subjects will receive PPC-06 400 mg QD, PPC-06 400 mg BID, PPC-06 600 mg BID, or Placebo BID from Week 6 through Week 24, based on the treatment arm to which they were randomized. Subjects will return to the clinic every 4 weeks (± 3 days) thereafter for drug accountability and to undergo safety and efficacy evaluations per the schedule of assessments ([Table 1-1](#)).

- Visit 4: End of Week 8
- Visit 5: End of Week 12
- Visit 6: End of Week 16
- Visit 7: End of Week 20
- Visit 8: End of Week 24
- Visit 9: End of Week 25

Table 6-1 Treatment Schedule - Titration Period (Weeks 1-5)

	400 mg QD	400 mg BID	600 mg BID	Placebo BID
Week 1 (Days 1-7)	100 P (am) + 100 P (am) 100 P (pm) + 100 (pm)	100 P (am) + 100 P (am) 100 P (pm) + 100 (pm)	100 (am) + 100 P (am) 100 P (pm) + 100 (pm)	100 P (am) + 100 P (am) 100 P (pm) + 100 P (pm)
Week 2 (Days 8-14)	200 P (am) + 200 P (am) 200 P (pm) + 200 (pm)	200 P (am) + 200 P (am) 200 P (pm) + 200 (pm)	200 (am) + 200 P (am) 200 P (pm) + 200 (pm)	200 P (am) + 200 P (am) 200 P (pm) + 200 P (pm)

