## 12.4 Study Medication Exposure and Compliance

The following exposure and compliance parameters will be summarized by treatment group and study period (overall, titration, and treatment as applicable) using descriptive statistics:

- Total number of days exposed to study medication, defined as date of last dose of study drug during the study minus date of first dose of study drug plus 1.
- Total number of tablets taken during the titration period (Week 1 – 5), defined as number of dispensed tablets from blister wallets minus number of returned tablets from blister wallets.
- Total number of tablets taken during the treatment period (Week 6 – 24), defined as total number of dispensed tablets from bottles minus total number of returned tablets from bottles.
- Number of tablets per bottle taken during the treatment period (Week 6 – 24), defined as number of dispensed tablets per bottle (total of 4 bottles per visit) minus number of returned tablets per bottle.
- Total number of tablets taken, defined as the summation of number of tablets taken during the titration and treatment period.
- Percent compliance will be calculated as the number of tablets taken divided by the expected number of tablets, defined for the titration period, treatment period, and overall. The expected number of tablets are as following:

Period	Number of Tablets Dispensed Per Dosing Regimen	Expected Total Number of Tablets
Titration (Week 1 – 5)	Week 1 – 4: 28 per week Week 5: 35 per week	$28*4 + 35 = 147$
Treatment (Week 6 – 24)	42 per week	$42*19 = 798$
Overall (Week 1 – 24)		945

- Subject compliance, defined as 80% - 120% (inclusive) in percent compliance. If the percentage of study medication compliance is unknown, the subject is assumed to be non-compliant with study medication. Subject compliance is summarized by periods and overall. Overall compliance will be the main determinant of compliance.
- Average daily dose of IP received can be calculated as the number of tablets divided by the number of days exposed to study medication. The average daily dose of IP received by each subject will be summarized by treatment group using summary statistics for the overall period.

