[1] Titration period TEAEs include all AEs starting or worsening after the first dose of study drug and before Day 15. Titration period duration is number of days between date of first study medication and the earlier of date of last study medication and Day 14 inclusive.

[2] Titration period TEAEs include all AEs starting or worsening after the first dose of study drug and before Day 36. Titration period duration is number of days between date of first study medication and the earlier of date of last study medication and Day 35 inclusive.

[3] Number of subjects with AEs divided by total number of subject-days with exposure to study medication, defined as sum of duration in days across all subjects in titration period.

Generated on XX/XX/XX:XXXX by SMYAE / Uses: XXXX / Reference: Listing XXXX

*Repeat for*

Table 14.3.1.1.2: Overall Summary of Adverse Events by Treatment  
Treatment Period  
Safety Population

*Programming note: modify footnotes as following:*

---

[1] Treatment period TEAEs include all AEs starting or worsening on or after Day 15. Treatment period duration is number of days between Day 15 and date of last study medication inclusive.

[2] Treatment period TEAEs include all AEs starting or worsening on or after Day 36. Treatment period duration is number of days between Day 36 and date of last study medication inclusive.

[3] Number of subjects with AEs divided by total number of subject-days with exposure to study medication, defined as sum of duration in days across all subjects in treatment period.

Table 14.3.1.1.3: Overall Summary of Adverse Events by Treatment  
Overall  
Safety Population

	PPC-06 400 mg QD (N=XX)	PPC-06 400 mg BID (N=XX)	PPC-06 600 mg BID (N=XX)	Placebo (N=XX)
Adverse Events				
Number of Events	XX	XX	XX	XX
Number of Subjects, n (%)	XX (XX.X)	XX (XX.X)	XX (XX.X)	XX (XX.X)
Exposure-adjusted incidence rate [1]	XX	XX	XX	XX
Treatment-Emergent Adverse Events (TEAEs)				
Number of Events	XX	XX	XX	XX
Number of Subjects, n (%)	XX (XX.X)	XX (XX.X)	XX (XX.X)	XX (XX.X)
Exposure-adjusted incidence rate [1]	XX	XX	XX	XX
Treatment-Related TEAEs				
Number of Events	XX	XX	XX	XX
Number of Subjects, n (%)	XX (XX.X)	XX (XX.X)	XX (XX.X)	XX (XX.X)
Exposure-adjusted incidence rate [1]	XX	XX	XX	XX
Serious TEAEs				
Number of Events	XX	XX	XX	XX
Number of Subjects, n (%)	XX (XX.X)	XX (XX.X)	XX (XX.X)	XX (XX.X)
Exposure-adjusted incidence rate [1]	XX	XX	XX	XX
Serious AEs (non-Fatal)				
<etc.>				

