[1] Study day is calculated relative to the date of first study drug administration (Day 1).

Generated on XX/XX/XX:XXXX by XXXXXX / Uses: XX

Listing 16.2.5.2 Study Drug Accountability – Bottles  
 All Randomized Subjects  
 [PPC-06 400 mg QD] [ PPC-06 400 mg BID] [ PPC-06 600 mg BID] [Placebo]

Subject Number	Kit Number	Bottle Number	Date (Day) Returned [1]	Number of Tablets		
				Dispensed	Returned	Used
XX-XXX	XXXXXXXX	AM1	DDMMMYYYY(XX)	30	XX	XX
		AM2	DDMMMYYYY(XX)	60	XX	XX
		PM1	DDMMMYYYY(XX)	30	--	--
		PM2	DDMMMYYYY(XX)	60	XX	XX
XX-XXX	XXXXXXXX	DDMMMYYYY(XX)	DDMMMYYYY(XX)	XX	XX	XX
		DDMMMYYYY(XX)	DDMMMYYYY(XX)	XX	XX	XX
		DDMMMYYYY(XX)	DDMMMYYYY(XX)	XX	XX	XX
		DDMMMYYYY(XX)	DDMMMYYYY(XX)	XX	XX	XX

[1] Study day is calculated relative to the date of first study drug administration (Day 1).

Generated on XX/XX/XX:XXXX by XXXXXX / Uses: XX

Listing 16.2.5.3: Study Drug Exposure and Compliance  
All Randomized Subjects  
[PPC-06 400 mg QD] [ PPC-06 400 mg BID] [ PPC-06 600 mg BID] [Placebo]

Subject Number	Study Period	Total # of Days Exposed [1]	Total # of Expected Tablets	Total # of Tablets Taken [2]	Average Daily Dose of IP [3]	Compliance	
						%Compliance [4]	Compliant?
XX-XXX	Overall	XX	945	XX	XX	XX.X	Yes
	Titration	-	147	XX	-	XX.X	No
	Treatment	-	798	XX	-	XX.X	Yes
XX-XXX	Overall	XX	945	XX	XX	XX.X	No
	Titration	-	147	XX	-	XX.X	Yes
	Treatment	-	798	XX	-	XX.X	Yes

Note: Titration Period: Week 1 – 5. Treatment Period: Week 6 – 24. Overall: Week 1 – 24.

[1] Defined as date of last dose of study drug during the study minus date of first dose of study drug plus 1.

[2] Defined as the summation of number of tablets taken during the titration, treatment, or overall period.

[3] Calculated as the number of tablets divided by the number of days exposed to study medication for the overall period.

[4] Calculated as the number of tablets taken divided by the expected number of tablets, defined for the titration period, treatment period, and overall.

Generated on XX/XX/XX:XXXX by XXXXX / Uses: XX

Listing 16.2.6.1.1: Psoriasis Area and Severity Index (PASI) Score  
 All Randomized Subjects  
 [PPC-06 400 mg QD] [ PPC-06 400 mg BID] [ PPC-06 600 mg BID] [Placebo]

Subject Number	Analysis Visit	Date (Study Day) [1]	Type	Head and Neck	Upper Limbs	Trunk	Lower Limbs	Scores
XXX-XXX	Baseline	DDMMYYYYY(XX)	Erythema	X	X	X	X	XX
			Induration	X	X	X	X	XX
			Scaling	X	X	X	X	XX
			Sum (E+I+S)	X	X	X	X	XX
			Area Involved	X	X	X	X	
			Sum X Area	XX	XX	XX	XX	XX.X

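### In the two period-split AE tables (14.3.1.1.1 and 14.3.1.1.2), 400 mg QD and the BID arms are summarised over different windows under one label, so QD-versus-BID comparisons there are not like for like

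*SAP*

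**What the plan says.** Protocol 4.1 describes a 24-week treatment phase that "includes a 5-week titration phase and a 19-week treatment period at the maintenance dose", with no exception by arm. Protocol 6.2 uses Weeks 1-5 for titration in all four arms. SAP 12.4 applies the same window to tablet counts and compliance, Table 14.1.3.2 carries it in its title, and the note to Listing 16.2.5.3 reads "Note: Titration Period: Week 1 – 5. Treatment Period: Week 6 – 24. Overall: Week 1 – 24".

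SAP 12.9.1 uses another definition for adverse events. For 400 mg QD, "Any TEAE starting before Day 15 is considered as a titration period AE"; for 400 mg BID and 600 mg BID the cut is Day 36. Tables 14.3.1.1.1 and 14.3.1.1.2 print all three doses side by side as titration period and treatment period. SAP 13, which lists changes from the protocol, mentions only the PP PGA analysis.

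For placebo, SAP 12.9.1 first says that no period will be designated, then asks for phases equivalent to the active arms: "for 400 mg it should be Day 15 and >15 days, for other doses it should be Day 36 and >36 days". The shells have two placebo columns. The footnote shared by 400 mg QD and the first of them reads "Titration period TEAEs include all AEs starting or worsening after the first dose of study drug and before Day 15", and the treatment-period footnote starts on Day 15 itself. The Day 36 footnotes follow the same pattern.

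**The concern.** Tolerability is a secondary objective and the trial studies three doses, so readers will compare AE figures across the dose columns. In these two tables the QD titration column covers 14 days and the BID columns 35. The QD treatment column includes Days 15-35, which the BID columns leave out. A difference between QD and BID could then come from window length and calendar time alone.

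The shared label adds to the risk. Someone who moves from the exposure table to the AE table meets the same period name with a different meaning for one arm, and no statement that it has changed.

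The placebo sentence raises a smaller issue. Read literally, it puts Day 15 (or Day 36) in titration for placebo, while the active-arm rules and the footnotes put that day in treatment. Two programmers could assign placebo events with onset on that day differently.

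**Working it through.** **1. The plan's own window.** SAP 12.4 gives the expected tablets as 28 × 4 + 35 = 147 for titration and 42 × 19 = 798 for treatment, and 147 + 798 = 945 overall. These reproduce exactly. They correspond to 5 × 7 = 35 days and 19 × 7 = 133 days in every arm.

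**2. Where the AE cut comes from.** Active mg per day, added up from Protocol Tables 6-1 and 6-3:

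| Arm | Weeks 1, 2, 3, 4, 5 | Week 6 on | First day at assigned daily dose |
|---|---|---|---|
| 400 mg QD | 100, 200, 400, 400, 400 | 400 | Day 15 |
| 400 mg BID | 100, 200, 300, 400, 600 | 800 | Day 36 |
| 600 mg BID | 200, 400, 600, 800, 1000 | 1200 | Day 36 |

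The cuts in SAP 12.9.1 match the last column.

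**3. Window lengths for a 168-day completer.** QD has 14 days of titration and 168 − 14 = 154 of treatment. BID has 35 and 168 − 35 = 133. The BID titration window is 35/14 = 2.5 times as long.

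**4. What the tables would show with no true difference.** The documents give no AE rates, so the daily hazard λ is an assumption, equal in all arms and constant over time, with no dropout. The chance of at least one AE onset in a window of T days is p = 1 − exp(−λT). SAP 12.9.1 defines the exposure-adjusted rate as subjects with an AE over total subject-days, which is p/T here.

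| λ per day | Titration %, QD vs BID | Rate ratio QD/BID, titration | Treatment %, QD vs BID | Rate ratio QD/BID, treatment |
|---|---|---|---|---|
| 0.002 | 2.8 vs 6.8 | 1.02 | 26.5 vs 23.4 | 0.98 |
| 0.01 | 13.1 vs 29.5 | 1.11 | 78.6 vs 73.6 | 0.92 |
| 0.05 | 50.3 vs 82.6 | 1.52 | 100.0 vs 99.9 | 0.86 |

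For example, at 0.01: 1 − exp(−0.14) = 13.1% and 1 − exp(−0.35) = 29.5%; the rate ratio is (0.131/14)/(0.295/35) = 1.11.

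The rate depends on window length because each subject counts once in the numerator while all exposure days stay in the denominator.

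**5. Hazard higher early.** Let the hazard be h1 in Days 1-35 and h2 afterwards, again equal across arms. The cumulative treatment-period hazard is 21·h1 + 133·h2 for QD and 133·h2 for BID.

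| h1, h2 per day | Treatment %, QD vs BID | Rate ratio QD/BID |
|---|---|---|
| 0.02, 0.01 | 82.6 vs 73.6 | 0.97 |
| 0.03, 0.01 | 85.9 vs 73.6 | 1.01 |
| 0.03, 0.005 | 72.6 vs 48.6 | 1.29 |

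The QD percentage is higher in each row. The rate ratio can fall on either side of 1.

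**6. The placebo day.** Counting Day 15 or Day 36 as titration lengthens the window by 1/14 = 7% or 1/35 = 3%. At 0.01 per day, placebo titration incidence moves from 13.1% to 13.9%, or from 29.5% to 30.2%.

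**7. Common window.** With Days 1-35 and Day 36 onward for every arm, window lengths are equal and every ratio in step 4 becomes 1.00.

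**The case against.** The strongest reply is that the QD cut is no slip. Table 6-1 brings that arm to its assigned daily dose on Day 15, and Protocol 4.1 describes the treatment period as time at the maintenance dose. Splitting each arm where it reaches its dose is a sensible way to look at tolerability, whereas the Weeks 1-5 definition suits tablet counts because every arm takes five weeks of blister wallets. A common Day 36 split would count three weeks of QD at its assigned dose as titration. Protocol 8.10 also lets the SAP prevail where the two differ. All of this stands, and it is why the dose-specific split should stay. It does not make the QD and BID columns comparable, and it does not explain one label with two meanings inside the SAP.

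A reader might go further and infer that AE figures across doses in general are not comparable. The documents do not support that. Each active arm has a placebo column on its own window, and the two BID arms share a window throughout. Table 14.3.1.1.3 and Tables 14.3.1.2 to 14.3.1.4 are not split by period. The footnotes also print the windows.

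A reader might also infer that the QD treatment-period rate is bound to look inflated. Events per day, (21·h1 + 133·h2)/154 against h2, would be 14%, 27% and 68% higher for QD in the three scenarios of step 5, but the SAP does not report that rate. Its subject-based rate gives 0.97, 1.01 and 1.29, and 0.92 at a constant 0.01.

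On placebo, the stated intention is to match the active arms, the day numbers are given only as an example, and the footnotes are already consistent. What remains is a wording correction.

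**Conclusion.** The point holds for QD versus BID in Tables 14.3.1.1.1 and 14.3.1.1.2 and nowhere else. There, counts and percentages are over unlike windows, and the exposure-adjusted rate only partly corrects for it. The clearest distortion is in titration percentages, where an equal hazard of 0.01 per day would show the lowest dose with fewer than half as many affected subjects as the BID arms. In the treatment period, the direction of the distortion in the rate depends on how the hazard changes over time.

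These sizes rest on assumed hazards that are equal across arms and on no dropout. They show what the tables could display without a true difference; they do not predict results. The differing window lengths and the undeclared change of definition come straight from the documents and need no assumption. This is a matter of descriptive safety reporting and does not touch the efficacy analyses.

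**What to change.** - Keep the dose-specific split, relabel it as before/after reaching assigned dose, and declare it with its reason in SAP 13.
- Add a summary with one calendar split for all four arms, Days 1-35 and Day 36 onward, and use it for comparisons between doses. Which display leads is a matter of preference; both should be available.
- Correct the placebo text in SAP 12.9.1 to before Day 15 / on or after Day 15 (to match 400 mg QD, naming QD) and before Day 36 / on or after Day 36 (to match the BID arms), as in the shell footnotes. Remove the statement that placebo has no designated period, and extend the exposure-adjusted rate definition, now limited to the three active arms, to the placebo columns that already display it.

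The cost is SAP wording and two extra summary tables. No new data are needed and trial conduct does not change.

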[Programming Note: include summaries for questions "The percent work time missed due to psoriasis", "The percent impairment while working due to psoriasis", "The percent overall work impairment due to psoriasis" and "The percent activity impairment due to psoriasis"]

Table 14.2.3.5: Analysis of Quality of Life Outcome  
 Summary of HEOR Score by Visit  
 Full Analysis Set, OC

	PPC-06 400 mg QD (N=XX)	PPC-06 400 mg BID (N=XX)	PPC-06 600 mg BID (N=XX)	Placebo (N=XX)
# of times visited physician's office or urgent care clinic				
Baseline				
N	XX	XX	XX	XX
Mean (SD)	XX.X (XX.X)	XX.X (XX.X)	XX.X (XX.X)	XX.X (XX.X)
Median	XX	XX	XX	XX
Minimum, Maximum	XX, XX	XX, XX	XX, XX	XX, XX
Week 12				
N	XX	XX	XX	XX
Mean (SD)	XX.X (XX.X)	XX.X (XX.X)	XX.X (XX.X)	XX.X (XX.X)
Median	XX	XX	XX	XX
Minimum, Maximum	XX, XX	XX, XX	XX, XX	XX, XX

<Repeat for Week 16, Week 24>

<Repeat for: "# of times visited other health care professionals", and "# of times received care from a health professional in your home">

Note: HEOR = Health Economics and Outcomes Research. OC = Observed Cases.

Generated on XX/XX/XX:XXXX by XXXXX / Uses: XXXX / Reference: Listings XXXX

Table 14.3.1.1.1: Overall Summary of Adverse Events by Treatment  
Titration Period  
Safety Population

	PPC-06 400 mg QD (N=XX)[1]	Placebo– Definition 1 (N=XX) [1]	PPC-06 400 mg BID (N=XX)[2]	PPC-06 600 mg BID (N=XX)[2]	Placebo– Definition 2 (N=XX) [2]
Adverse Events					
Number of Events	XX	XX	XX	XX	XX
Number of Subjects, n (%)	XX (XX.X)	XX (XX.X)	XX (XX.X)	XX (XX.X)	XX (XX.X)
Exposure-adjusted incidence rate [3]	XX	XX	XX	XX	XX
Treatment-Emergent Adverse Events (TEAEs)					
Number of Events	XX	XX	XX	XX	XX
Number of Subjects, n (%)	XX (XX.X)	XX (XX.X)	XX (XX.X)	XX (XX.X)	XX (XX.X)
Exposure-adjusted incidence rate [3]	XX	XX	XX	XX	XX
Treatment-Related TEAEs					
Number of Events	XX	XX	XX	XX	XX
Number of Subjects, n (%)	XX (XX.X)	XX (XX.X)	XX (XX.X)	XX (XX.X)	XX (XX.X)
Exposure-adjusted incidence rate [3]	XX	XX	XX	XX	XX
Serious TEAEs					
<etc.>					
Serious AEs (non-Fatal)					
<etc.>					
Death					
<etc.>					
AEs Leading to Study Drug Discontinuation					
<etc.>					

Note: For each treatment, a subject will be counted once only within each AE category.

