Death				
<etc.>				
AEs Leading to Study Drug Discontinuation				
<etc.>				

Note: For each treatment, a subject will be counted once only within each AE category. TEAEs include all AEs starting or worsening after the first dose of study drug.

[1] Number of subjects with AEs divided by total number of subject-days with exposure to study medication, defined as sum of duration in days across all subjects during the study period.

Generated on XX/XX/XX:XXXX by SMYAE / Uses: XXXX / Reference: Listing XXXX

Table 14.3.1.2: Summary of Treatment-emergent Adverse Events  
by System Organ Class and Preferred Term in Descending Frequency  
Safety Population

System Organ Class Preferred Term	PPC-06 400 mg QD (N=XX)	PPC-06 400 mg BID (N=XX)	PPC-06 600 mg BID (N=XX)	Placebo (N=XX)
Subjects with any TEAE, n (%)	XX (XX.X)	XX (XX.X)	XX (XX.X)	XX (XX.X)
<< Adverse Event System Organ Class >>	XX (XX.X)	XX (XX.X)	XX (XX.X)	XX (XX.X)
<< Adverse Event Preferred Term >>	XX (XX.X)	XX (XX.X)	XX (XX.X)	XX (XX.X)
<< Adverse Event Preferred Term >>	XX (XX.X)	XX (XX.X)	XX (XX.X)	XX (XX.X)
<< Adverse Event Preferred Term >>	XX (XX.X)	XX (XX.X)	XX (XX.X)	XX (XX.X)
<< Adverse Event System Organ Class >>	XX (XX.X)	XX (XX.X)	XX (XX.X)	XX (XX.X)
<< Adverse Event Preferred Term >>	XX (XX.X)	XX (XX.X)	XX (XX.X)	XX (XX.X)
<< Adverse Event Preferred Term >>	XX (XX.X)	XX (XX.X)	XX (XX.X)	XX (XX.X)
<< Adverse Event Preferred Term >>	XX (XX.X)	XX (XX.X)	XX (XX.X)	XX (XX.X)

Note: Counts reflect numbers of subjects reporting one or more adverse events that map to MedDRA system organ class or preferred term. A subject may be counted once only in each row of the table.

Generated on XX/XX/XX:XXXX by SMYTEAEPT / Uses: XXXX / Reference: Listings XXXX

<Programming Note: sort by SOC in alphabetical order and PT in descending order of the combined frequency in the three active treatments>

Table 14.3.1.3: Summary of Treatment-emergent Adverse Events  
 by System Organ Class, Preferred Term, and Maximum Severity  
 Safety Population

System Organ Class Preferred Term	Severity	PPC-06 400 mg QD (N=XX)	PPC-06 400 mg BID (N=XX)	PPC-06 600 mg BID (N=XX)	Placebo (N=XX)
Subjects with any TEAE, n (%)	Total	XX (XX.X)	XX (XX.X)	XX (XX.X)	XX (XX.X)
	Mild	XX (XX.X)	XX (XX.X)	XX (XX.X)	XX (XX.X)

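### The exposure-adjusted AE rate counts each subject once but divides by exposure that continues after the first event, so for common AE rows it depends on AE frequency, period length and who stops drug

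*SAP*

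**What the plan says.** SAP 12.9.1 defines the rate as "number of subjects with AEs divided by total number of subject-days with exposure to study medication". The denominator is spelled out: "Total number of subject-days with exposure in each period = sum of durations in days across all subjects in each period". Durations run to the last dose or the end of the period. For the BID arms, "Treatment period = Number of days between Day 36 and date of last study application inclusive"; for the QD arm, "Treatment period = Number of days between Day 15 and date of last study application inclusive". Titration runs to Day 14 for 400 mg QD and to Day 35 for both BID arms.

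The shells agree. Footnote [3] of Table 14.3.1.1.1 reads "Number of subjects with AEs divided by total number of subject-days with exposure to study medication", and the note above it says "For each treatment, a subject will be counted once only within each AE category". In Table 14.3.1.1.3 the overall denominator is "defined as sum of duration in days across all subjects during the study period". No text stops a subject's exposure at the first event.

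The rows that receive the rate are any AE, any TEAE, serious TEAE, treatment-related TEAE, TEAE leading to study drug discontinuation, non-fatal SAE and death. The tables by system organ class and preferred term show only counts and percentages.

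On placebo, text and shells differ. The text says "For the 3 arms receiving active treatment, exposure-adjusted incidence rate will be defined for both titration and treatment periods". The shells for the titration and treatment periods also show the rate in two placebo columns, one for each period definition, and the overall table shows it for placebo as well.

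**The concern.** After a first AE in a category, a subject can add nothing more to the numerator but goes on adding days to the denominator. A first-event incidence rate would stop that subject's clock at the event. An event rate would keep the full exposure but count every event. The planned measure takes its numerator from one and its denominator from the other.

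The excess denominator grows with the share of subjects who have an event and with how long they stay on drug afterwards, and both can differ by arm. Safety and tolerability is a secondary objective. Protocol 7.5.1.4 describes GI disorders and flushing as commonly observed, so the any-AE, any-TEAE and related-TEAE rows may be well filled. Readers will compare the columns, and a difference between two of them could reflect the formula instead of the drug.

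**Working it through.** **Inputs from the documents.** Full treatment is 24 weeks, or 24 × 7 = 168 days. Titration is 14 days (QD) or 35 days (BID). The treatment period for a subject dosed to Day 168 is 168 − 14 = 154 days (QD) or 168 − 35 = 133 days (BID). SAP section 7 assumes 50% dropout. The documents state no expected AE incidence or value of this rate, so there is no planned figure to reproduce. AE incidences, hazards and stopping fractions below are assumptions.

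**Step 1: equal follow-up, no dropout.** With a constant first-event hazard h over T days, the proportion with an event is p = 1 − exp(−hT).

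- Planned rate = p / T
- First-event rate = h = −ln(1 − p) / T
- Planned / first-event = p / (−ln(1 − p))

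For p = 0.70 this is 0.70 / 1.204 = 0.58, and for p = 0.40 it is 0.40 / 0.511 = 0.78. The planned drug-placebo ratio is the risk ratio, 0.70 / 0.40 = 1.75. The first-event ratio is 1.204 / 0.511 = 2.36.

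| Assumed incidence, drug / placebo | Understatement, drug / placebo | Planned ratio | First-event ratio |
|---|---|---|---|
| 3% / 1% | 2% / 1% | 3.00 | 3.03 |
| 10% / 5% | 5% / 3% | 2.00 | 2.05 |
| 60% / 40% | 35% / 22% | 1.50 | 1.79 |
| 70% / 40% | 42% / 22% | 1.75 | 2.36 |
| 80% / 50% | 50% / 28% | 1.60 | 2.32 |
| 90% / 60% | 61% / 35% | 1.50 | 2.51 |

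**Step 2: 50% dropout unrelated to AEs.** A simulation with 400,000 subjects per arm over 168 days gives planned against first-event ratios of 1.53 and 1.80 (60%/40%), 1.68 and 2.33 (80%/50%), and 1.60 and 2.51 (90%/60%). The shrinkage persists.

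**Step 3: stopping drug after the first AE.** The same simulation at 60%/40%, with 20% other dropout, 5% of placebo AE subjects stopping, and stops made within 7 days of the event:

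| Share of drug-arm AE subjects who stop | Discontinued, drug / placebo | Planned ratio | First-event ratio |
|---|---|---|---|
| 50% | 43% / 21% | 1.77 | 1.79 |
| 70% | 53% / 22% | 1.92 | 1.80 |

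In the second row placebo is understated more than drug (20% against 15%), so the direction reverses. At 80%/50%, 70% stopping gives 2.35 against 2.32; at 90%/60% it gives 2.47 against 2.52. The first-event ratio barely moves, because the underlying hazards have not changed.

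**Step 4: unequal period lengths at one hazard.** Take h = 0.02 per day in both arms.

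- QD titration: (1 − e^(−0.28)) / 14 = 0.0174 per day
- BID titration: (1 − e^(−0.70)) / 35 = 0.0144 per day

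The BID rate is about 18% lower (0.0144 / 0.0174 ≈ 0.82) with no difference in hazard. The two placebo columns would disagree for the same reason. With person-time stopped at the first event, both give 0.020.

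**The case against.** **Direction.** A reader might infer that the formula always flatters the active arms. The documents do not support that. They foresee permanent discontinuation for unresolved GI intolerance (SAP section 3) and assume 50% dropout, and Step 3 shows that heavy stopping at the first AE in the drug arm can remove or reverse the shrinkage. This part of the objection stands. It also shows why the measure is unstable: its ratio moves with stopping behaviour while the hazards stay fixed.

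**Early events.** A reader might infer a larger effect because these events tend to come early. At 70% versus 40%, with 120 days' mean exposure, onset at Day 15 gives 0.7 / (0.7 × 15 + 0.3 × 120) against 0.4 / (0.4 × 15 + 0.6 × 120), a ratio of 2.94; onset at Day 30 gives 2.58. The documents give no onset times. The figures could apply only to the overall table, because the titration and treatment tables cap the period. Under the constant-hazard 70%/40% case, the planned ratio would be 2.29 (14 days) or 2.20 (35 days) in titration and 1.79 to 1.85 in treatment, against 2.36. Under early onset the first-event ratio also depends on exposure: at Day 15 onset it is 2.58 with 60 days, 2.94 with 120 and 3.07 with 168. It is therefore not a fixed true value, and no weight is placed on these figures.

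**Purpose.** A reader might say the rate was added to correct for unequal dropout and fails at that. The SAP gives no reason for including it.

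**Consequence.** No ratio, difference or test of this rate is planned. The formula is footnoted, the same tables show event counts and percentages, and onset days are listed, so a first-event rate could be recovered. GI and flushing terms have no rate of their own and enter only through the pooled rows. For deaths and discontinuation TEAEs, exposure ends at about the event. All of this stands and limits the point to the common rows of a descriptive summary.

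**Conclusion.** The definition should be corrected, with limited consequence. It is certain from the text that subjects are counted once while exposure after the first event is retained. For any AE, any TEAE and treatment-related TEAE, the planned rate falls below the first-event rate by an amount set by AE frequency, period length and who stops drug after an AE. Across the assumed incidences of 40% to 90% with no dropout, the shortfall is 22% to 61%. The effect on the drug-placebo comparison is conditional: toward the risk ratio when discontinuation is similar across arms, little or reversed when drug-arm subjects often stop at their first AE. Comparisons between QD and BID titration, and between the two placebo columns, are distorted by period length alone.

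The sizes rest on constant hazards and on assumed incidences and stopping fractions. The co-primary analyses are unaffected.

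**What to change.** In SAP 12.9.1 and the footnotes of Tables 14.3.1.1.1 to 14.3.1.1.3, define each subject's person-time, for each category and period, as the days from the start of the period to the first event in that category, or to the end of period exposure if there is no event or if that end comes earlier. The last clause also covers TEAEs that start in the 5 days after the last dose, which count as treatment-emergent although exposure has ended.

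State the same definition for placebo, including both period definitions, so that the text matches the shells.

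If total exposure is kept as a denominator, pair it with the number of events and label the result an event rate.

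The cost is a wording change and one small derivation. AE onset dates are already collected and listed.
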